All SAEs will be assessed by the study Sponsor to determine if an event is anticipated or unanticipated. The source of information that will be utilized in the determination of expectedness will include the HITCH Drug Information Report, the HITCH Informed Consent, published literature, and the FDA Adverse Event Reporting System (AERS). SAEs found by the Sponsor to be both related to the investigational treatment and unexpected will be reported to the VA Chief Research and Development Officer, the FDA, and site investigators after review by the Study Chairs, VA Central IRB, the CSPCRCC Director and the Perry Point CSPCC Director.

Reporting of Adverse and Serious Adverse Events to the DMC

The HITCH Biostatisticians, with coordination from CSPCRPCC, will tabulate and summarize all study intervention related AEs and all SAEs (intervention related or not related) for the DMC on a schedule set by the DMC, but no less than annually. The DMC will also determine when the committee should be unblinded to treatment assignment in reviewing AE/SAE data. The DMC will advise the CSP Director whether the study should continue or be stopped for safety reasons.

Reporting Requirements of the VA Central or Local IRB

Sites are additionally responsible for following the VA Central IRB policy in submitting safety data, unanticipated serious problems, and protocol deviations. The VA Central IRB's most recent policy including a Table of Reporting Requirements, instructions, and forms can be found at <http://www.research.va.gov/vacentralirb/policies.cfm>.

VHA Handbook 1058.01 requires that the VA CIRB must be notified orally and immediately upon becoming aware of any research death that is both unanticipated and related (includes possibly related) to the research. In addition to the oral notification, site personnel must also ensure that a written notification is sent to the VA CIRB within 5 business days of becoming aware of the death (Note: this is different than the 3 calendar day reporting requirement to CSP).

Reporting to the FDA

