9. SAFETY MONITORING

Data and Safety Monitoring Plan

The VA Clinical Sciences Research and Development (CSR&D) centralized Data Monitoring Committee (DMC) will monitor this study. The CSR&D DMC provides an ongoing independent evaluation of the progress of studies, including patient accrual and retention, adverse events monitoring, and analysis plan. This is a service that is provided by CSR&D to ensure independent oversight of the safety and integrity of this project. No other DMC or Data and Safety Monitoring Board (DSMB) review is needed.

The DMC office is located within the Cooperative Studies Program Coordinating Center (CSPCC) at the Edward Hines, Jr. VA Hospital in Hines, IL. The DMC Office at Hines then communicates directly with the PI to provide DMC related information.

After the DMC has recommended approval for this trial to begin and the first patient has been randomized, a progress report will be due in approximately one month and then monthly thereafter. The PI typically will not need to call in for the DMC review after the

initial review. The DMC makes recommendations to the director of CSR&D for endorsement. The recommendations range from approval (unconditionally or with conditions to be addressed) to probation to termination.

Following each DMC meeting, the PI will receive meeting minutes containing any action items for which a response will be requested typically within 30 days. Then the process starts all over again for the next reporting period. In addition to the quarterly progress reports, all Serious Adverse Events are to be reported to the DMC.

Additional Safety Monitoring for AEs of Special Interest

Whereas the DMC serves as the entity with primary oversight responsibility for the study, additional real-time monitoring will be conducted to capture AEs of special interest, including cardiac arrhythmias and thromboembolic events that may result from degarelix. In particular, cardiac arrhythmias and thromboembolic complications of grades 3-5 according to CTCAE v5.0 (see Appendix C) will be closely monitored through not only ongoing, daily review of AE and SAE reports, but also through regular, planned teleconference calls to include:

- The study chair ([name]), co-chair ([name]), and the lead site coordinator ([name]),
- One or more investigators from each site and/or one or more site coordinators.

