50%	Degarelix + BSC	64	72	84
	Placebo + BSC	32	36	42
	Total	96	108	126

Duration of Study and Number of Participating Sites

To estimate the expected study duration and resources, we assume that the recruitment rate will be half of what we anticipate. Under this assumption, various scenarios were examined in order to identify an optimal combination between the number of sites, the study duration (which includes recruitment period and follow-up period) and the estimated budget. The study will include four VA medical centers and each center will randomize 17 patients per month on average; however, estimated recruitment rate will vary depending on the patient volume of each participating center as the disease evolves. Based on these assumptions, the recruitment period was found to be approximately three

months. This will be followed by approximately one month of follow up for the last patients randomized into the study followed by one month of data analysis. Thus, the study duration including start-up will be approximately five months.

Interim Analysis and Criteria for Study Termination

A mid-term interim analysis of the primary endpoint will be performed at half of the patients or 99 randomized patients complete or are terminated the study. If the mid-term analysis of the primary endpoint indicates that the null hypothesis can be rejected with a boundary value of 2.77 (standardized $Z > 2.77$ or < -2.77) at an α -level of 0.006 or accepted with a boundary value of 0.44 ($-0.44 \leq \text{standardized } Z \leq 0.44$) based on O'Brien and Fleming criteria, the study will be recommended for trial termination for efficacy and futility reasons (shown in the Figure 1). Enrollment will be paused if the interim analysis results indicate crossing of the threshold for futility or efficacy until the final DMC recommendation is rendered.

Meanwhile, the drug toxicity will be closely monitored and analyzed. As described in previous sections, arrhythmia and thromboembolic complications are adverse events of special interest that will be monitored closely and graded according to on CTCAE 5.0. Once the toxicity markers reach a threshold of 25% (Ray and Rai 2011), a statistical analysis of the toxicity will be performed. If the experimental (degarelix) group has a significant higher toxicity compared to the placebo group at an α -level of 0.01, then results will be reported to the DMC for a recommendation for trial termination.

[figure not shown]

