## 2.3 Study Design

This study is a parallel, double-blind, placebo controlled, superiority trial in which participants will be randomized to the degarelix + BSC treatment group or to the placebo + BSC control group. The study will randomize 198 Veterans at four VA Medical Centers at a 2:1 treatment assignment ratio, i.e. 132 participants in the degarelix group and 66 participants in the placebo group. The total recruitment period will be approximately 90 days with an approximately follow-up period of 60 days. The

duration of the study will be approximately five months. Informed consent for the study will be obtained prior to participants' enrollment eligibility screening. Randomization will be performed via an Interactive Web Response System (IWRS), a computerized system that will allow authorized study personnel to randomize patients and obtain study treatment assignments using a stratified random block method once a participant has eligible to the study. Study drug treatment will be given according to the randomization assignment within 48 hours after randomization. BSC consists of supplemental oxygen, antibiotics, vasopressor support, peritoneal or hemodialysis, antibiotics, intravenous fluids, etc. The participants will be followed up till their discharge. The study flow is shown in Appendix 5.2. Both the participants and the treating physicians/nurses as well site investigators/coordinators will be blinded of the treatment assignment.

Participants will be followed until death or discharge, whichever comes first. If a patient dies or refuses to continue participation, he will be terminated. A termination form will be used to record the termination information for these patients. If a patient remains hospitalized beyond day 30, the patient will continue to be followed for clinical endpoints, but no additional research labs will be obtained.

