#### 3.1.2 Analysis Conventions

This section details general policies to be used for the statistical analyses. Departures from these general policies may be given in the specific detailed sections of this statistical analysis plan. When this situation occurs, the rules set forth in the

specific section take precedence over the general policies. The following policies will be applied to all data presentations and analyses.

- All statistical tests will use a significance level of  $\alpha = 0.05$ . Two-tailed tests will be performed for all analyses that use statistical testing.
- All p-values will be rounded to 3 decimal places. All p-values that round to 0.000 will be presented as ' $<0.001$ ' and p-values that round to 1.000 will be presented as ' $>0.999$ '. Any p-value  $\leq \alpha$  will be considered statistically significant.
- Summary statistics will consist of the number and percentage of responses in each category for discrete variables, and the mean, median, standard deviation (SD), minimum, and maximum for continuous variables.
- All mean and median values will be formatted to one more decimal place than the measured value. Standard deviation values will be formatted to two more decimal places than the measured value.
- All percentages will be rounded to one decimal place. The number and percentage of responses will be presented in the form XX (XX.X), where the percentage is in the parentheses. The decimal of the percentage may be dropped due to space constraints when creating a table.
- All listings will be sorted for presentation in order of treatment group, site number, participant number, and date of procedure or event.
- All analysis and summary tables will have the population sample size for each treatment group in the column heading.
- Calculating change from baseline to a visit will be done as follows: change = visit –baseline.
- Baseline is defined as the last data point before the first treatment is administered. If baseline data are not available, screening data will be used.
- Version 9.4 of SAS® or higher will be the statistical software package used to produce all summaries, listings, statistical analyses, and graphs.
- Updated version of MedDRA will be used for adverse event and pre-treatment coding.

- The current version of the World Health Organization (WHO) drug dictionary will be used for the coding of medications.

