### 3.8.2. Drug Toxicity Analysis

The drug toxicity will be closely monitored and analyzed. Cardiac arrhythmia and thromboembolic complications are adverse events of special interest (grade 3 and above) that will be monitored closely and graded according to on CTCAE 5.0. Once the toxicity markers reach a threshold of 25%, a statistical analysis of the toxicity will be performed. The treatment difference will be analyzed initially with a Pearson  $\chi^2$  test using SAS PROC FREQ (Table 3.8.2.1) and logistic regression will also be performed using SAS PROC LOGISTIC by taking account of prognostic factors described in the primary endpoint analysis (Table 3.8.2.2). If the experimental (degarelix) group has a significant higher toxicity compared to the placebo group at an  $\alpha$ -level of 0.01, then results will be reported to the DMC for a recommendation for trial termination.

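### The by-arm toxicity comparison waits for an undefined 25% event rate, which severely weakens it if background rates of arrhythmia and thromboembolism are low

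*SAP*

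**What the plan says.** SAP 3.8.2 names the events: "Cardiac arrhythmia and thromboembolic complications are adverse events of special interest (grade 3 and above". The comparison starts on a condition, "Once the toxicity markers reach a threshold of 25" per cent, and protocol section 10 (Interim Analysis and Criteria for Study Termination) has the same condition. A second condition follows: "If the experimental (degarelix) group has a significant higher toxicity compared to the placebo group". The level for that test is 0.01, and only a result past it is referred to the DMC as possible grounds for ending the trial. SAP 3.1.2 makes the test two-sided: "Two-tailed tests will be performed for all analyses that use statistical testing".

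The documents leave open:
- whether 25% is a pooled rate or the degarelix-arm rate;
- whether the two event types count together or separately;
- the minimum number of patients, and how often the rate is checked.

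The adverse event collection window, which also bears on the rate, is 60 days after dosing in protocol section 8 and 30 days in SAP 2.5.3.

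On reporting to the DMC, protocol section 8 sets a minimum, "on a schedule set by the DMC, but no less than annually". Protocol section 9 first describes monthly progress reports and then says: "In addition to the quarterly progress reports, all Serious Adverse Events are to be reported to the DMC".

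**The concern.** A gate on the absolute event rate differs from a test of whether the arms differ. If these events are uncommon on placebo, degarelix could multiply them several-fold while the observed rate stays below 25%, and the pre-specified comparison would not be run.

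Every cardiovascular rate the protocol cites for degarelix is far below the gate: 3.4% ischemic events over 12 months of continuous therapy (section 1), with a lower frequency expected after one dose, and under 1% for QTcF above 500 msec (section 6).

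The rule is the only by-arm safety trigger that the plan fixes in advance. Each patient gets one dose and enrolment is planned for about 90 days, so a comparison that comes late can protect few patients.

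**Working it through.** **Inputs.** Arm sizes are "132 participants in the degarelix group and 66 participants in the placebo group" (SAP 2.3). The gate is 25%, and the test is two-sided at 0.01 in the harmful direction, so z must exceed 2.576. The plan states no operating characteristic for this rule, so there is no figure of its own to reproduce. All rate pairs below are assumptions.

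**What 25% requires.**
- Pooled: 0.25 × 198 = 49.5, so 50 patients with an event. Degarelix arm: 0.25 × 132 = 33 patients.
- At 2:1 the pooled rate is (2·D + P)/3, where D and P are the degarelix and placebo rates. Setting this to 0.25 gives D = (0.75 − P)/2. Degarelix then needs 35% if placebo is 5%, 32.5% if 10%, and 30% if 15%.

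**One concrete result.** Take 24/132 (18.2%) on degarelix and 3/66 (4.5%) on placebo. The pooled rate is 27/198 = 13.6%. Then z = (0.1818 − 0.0455)/√[0.1364 × 0.8636 × (1/132 + 1/66)] = 0.1364/0.0517 = 2.64. This passes the 0.01 test but opens the gate on neither reading.

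**At the half-way sample** (66 and 33), a pooled 25% is 25 events. The test then needs 22/66 against 3/33 (z = 2.62); 21/66 against 4/33 gives z = 2.13 and fails.

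**Probability that the rule fires, one look at 132/66.** With x events on degarelix and y on placebo, I summed Bin(x; 132, D) × Bin(y; 66, P) over all (x, y) with z > 2.576 and, where it applies, an observed rate of at least 25%.

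| Placebo vs degarelix (assumed) | No gate | Pooled gate | Degarelix-arm gate |
|---|---|---|---|
| 5% vs 15% | 26% | <0.01% | 0.2% |
| 5% vs 20% | 63% | 0.01% | 9% |
| 5% vs 25% | 88% | 0.8% | 52% |
| 10% vs 25% | 47% | 2.5% | 36% |
| 10% vs 30% | 76% | 24% | 74% |
| 15% vs 35% | 67% | 59% | 67% |
| 20% vs 40% | 61% | 61% | 61% |

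**Repeated checks** (20,000 simulated trials; no gate / pooled / degarelix arm).
- Looks at 66, 132 and 198 patients: 5% vs 15%, 28 / 0.0 / 1.5%; 5% vs 20%, 64 / 0.6 / 17%; 5% vs 25%, 89 / 6 / 61%.
- A check after every patient from the 20th: 5% vs 15%, 36 / 0.3 / 4%; 5% vs 20%, 72 / 3 / 29%.
- The same, with the gate staying open once crossed: the two gated figures become 4 / 15% and 17 / 49%.

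**The case against.** A reader might infer that the rule can almost never fire, or that it cannot detect the harms it was written for. The documents do not support that. They give no background rate for grade 3 or higher arrhythmia or thromboembolism in hospitalized COVID-19 patients. The 3.4% and under-1% figures come from 12 months of continuous degarelix therapy and concern ischemic events and QTcF prolongation, so they cannot stand in for that rate. If background rates are high, or the gate applies to the degarelix arm and that arm's rate is 25% or more, the rule keeps much or all of its power. The wording also suggests continuing surveillance, and repeated checks raise the gated figures. All of this stands.

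The gate is also not the only limit. At 5% vs 15% the ungated test flags only 26% of trials, so the 0.01 level and the sample size account for part of the weakness. The 25% is attributed to a cited paper on toxicity monitoring, which may define it, but the protocol and SAP do not carry a definition over.

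A reader might also infer that the DMC would see no harm at all. That goes too far. Special-interest events of grade 3-5 are reported within 3 calendar days (protocol section 8) and discussed on weekly calls (section 9). All SAEs go to the DMC, which decides when to be unblinded. None of this depends on the gate. But the calls involve study chairs, investigators and coordinators, and section 11 denies investigators unblinded data. Unblinding is at the DMC's discretion, and the by-arm tests in SAP 3.8.1 have no interim timing. These routes mitigate the gap without guaranteeing a comparison during enrolment.

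Finally, the annual wording in section 8 is only a minimum, which monthly reporting meets. The real conflict is monthly against quarterly within section 9.

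**Conclusion.** The point holds in a limited form. The 25% gate is undefined in its denominator, minimum sample and timing, and two statisticians could apply it differently. When background rates are low it removes most of the rule's sensitivity: at 5% vs 20%, from 63% to 0.01% (pooled) or 9% (degarelix arm) with one look. When background rates are high it costs little: at 15% vs 35%, from 67% to 59% or 67%. These sizes rest on assumed event rates, one look at the full 198 patients and a two-sided 0.01 test. More frequent checks narrow the gap at low rates but do not close it.

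**What to change.** Remove the 25% precondition for the by-arm comparison in SAP 3.8.2 and protocol section 10. In each scheduled DMC report, give counts by arm, the difference and its confidence interval for grade 3-5 special-interest events, with coded arms if the DMC prefers to stay blinded. Reconcile the monthly and quarterly wording in protocol section 9 so that one schedule applies, and reconcile the 60-day and 30-day collection windows so that the table has one definition. Leave any stopping threshold to the DMC.

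The cost is one extra table per report and more looks at the safety data, with some added risk of a chance imbalance drawing attention.

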## 3.9 Interim Analyses

A mid-term interim analysis of the primary endpoint will be performed when half of the participants (99 randomized participants) complete or are terminated from the study. If the mid-term analysis of the primary endpoint indicates that the null hypothesis can be rejected with a boundary value of 2.77 (standardized  $Z > 2.77$  or  $< -2.77$ ) at an  $\alpha$ -level of 0.006 or accepted with a boundary value of 0.44 ( $-0.44 \leq \text{standardized } Z \leq 0.44$ ) based on O'Brien and Fleming criteria, the study will be recommended for trial termination for efficacy and futility reasons (shown in Appendix 5.7). The number and percentage of participants with the composite endpoint at day 15 will be summarized and compared using Pearson  $\chi^2$  test (Table 3.9.1a) using SAS PROC FREQ. For

logistic regression analysis, if the coefficient for treatment effect is significant (i.e., the confidence interval for the odds ratio does not include 1), then the null hypothesis will be rejected. The significant level for each covariate coefficient in the model will best determined by Wald test (Table 3.9.1b) using SAS RPOC LOGISTIC. The analysis will be done in the ITT population. The detailed analysis is described in the primary endpoint analysis in the section 3.7.1.

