## 2.6 Sample Size Consideration

In a recent antiviral drug trial to treat adults hospitalized with severe COVID-19 published in the New England Journal of Medicine (NEJM) on March 18, 2020^32, the results showed that a mortality rate of 17%, hospital stay rate of 50%, and ECMO or mechanical intubation rate of 11% among the patients managed with BSC after two-week follow-up. In the current study, we propose a composite endpoint of mortality, ongoing need for hospitalization, and ECMO or mechanical intubation at 15 days after randomization. We are expecting to reduce the composite endpoint rate to 35% after the degarelix treatment plus BSC from 60% for patients treated placebo plus BSC.

The sample size estimation and power analysis shown in Table 2 are based on the hypothesis testing of the primary endpoint, which is the composite endpoint of mortality, hospital stay rate, and ECMO or mechanical intubation at 15 days after

randomization (Day 15). According to the composite endpoint outlined in the previous section, we assume that an effect size for the primary endpoint of 42% can be anticipated in the degarelix group. The other assumptions include a three-month accrual time and one-month follow-up time, and 2:1 sample allocation of degarelix: placebo treatment group. The sample size for the study is estimated based on a superiority trial design. To have 90% power of detecting the expected 42% reduction using a two-sided two proportion test with a significance level of 0.05 in the degarelix compared to the placebo group will require 186 evaluable patients total (i.e. 124 evaluable patients in the degarelix group and 62 evaluable patients in the placebo group). Based on an assumed 5% attrition rate, 198 patients will be required (i.e. 132 in the degarelix group and 66 in the placebo group) to achieve actual statistical significance at alpha level of 0.05 and power of 90% (Appendix 5.5).

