#### 3.7.1. Primary Endpoint Analysis

The primary study endpoint will be the composite outcome of mortality, ongoing need for hospitalization, and ECMO or mechanical intubation at 15 days after randomization. This outcome will be compared according to assigned treatment groups, using Pearson  $\chi^2$  test. The test for differences between the treatment groups in the primary outcome will be conducted at an overall  $\alpha$ -level of 0.05 (i.e.  $\alpha = 0.006$  for mid-term interim analysis,  $\alpha = 0.044$  for the final analysis). If a participant drops out from the study, then he will be considered as a failure. Additional analyses will be conducted using logistic models to adjust for other clinical factors, such as age, hypertension, and COPD. Logistic regression will be used for the primary endpoint ( $y = 1$  if a composite outcome, otherwise  $y = 0$ ) analysis with the treatment group as the testing factor ( $x$ ). The following covariates will be included in the model: age ( $z_1$ ), hypertension ( $z_2$ ), and COPD ( $z_3$ ). Given the composite outcome probability  $p = p(y = 1|x, z_1, z_2, z_3)$ , the basic model is defined as follows:

$$\text{Logit}(p) = \ln\left(\frac{p}{1-p}\right) = \beta_0 + \beta_1 x + \beta_2 z_1 + \beta_3 z_2 + \beta_4 z_3$$

Odds ratio and 95% confidence interval (CI) will be presented using SAS PROC GENMOD or PROC LOGSTIC. If the coefficient for treatment effect is significant, then the null hypothesis will be rejected. Logistic models will be tested for goodness of fit. We will assess goodness-of-fit using the statistic -2 log likelihood, which has a  $\chi^2$

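### The final test level of 0.044 is the alpha spent at the last look, not the matching p-value cut-off, so overall alpha is about 0.044 to 0.046 instead of 0.05 (a conservative error)

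*SAP*

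**What the plan says.** SAP 3.9 and the interim analysis part of Protocol section 10 plan one look at the primary endpoint when 99 of 198 randomised patients have finished. At that look the null hypothesis "can be rejected with a boundary value of 2.77" (attached to a level of 0.006) or "accepted with a boundary value of 0.44". Both values are attributed to O'Brien-Fleming criteria, and crossing either leads to a recommendation to terminate.

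SAP 3.7.1 and the primary endpoint analysis in Protocol section 10 give the decision levels for the Pearson chi-square test. The overall level is 0.05, made up of 0.006 "for mid-term interim analysis" and 0.044 for the final analysis. The text states no final critical Z.

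SAP 2.6 sizes the trial as a single-look test: "To have 90% power of detecting the expected 42% reduction using a two-sided two proportion test with a significance level of 0.05". It expects to "reduce the composite endpoint rate to 35% after the degarelix treatment plus BSC from 60% for patients treated placebo plus BSC" with "2:1 sample allocation of degarelix: placebo treatment group", which leads to "186 evaluable patients total (i.e. 124 evaluable patients in the degarelix group and 62 evaluable patients in the placebo group"). It adds: "Based on an assumed 5% attrition rate, 198 patients will be required". It describes no allowance for the interim look, the 0.044 level or the futility stop.

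**The concern.** The two levels add to 0.05 by plain subtraction: 0.05 − 0.006 = 0.044. That is a correct account of alpha spent per look. It is not the p-value at which the final test should be judged. The interim and final statistics are correlated, because the final data contain the interim data, so the nominal level that spends 0.044 at the last look is larger than 0.044.

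This is the pass/fail line of the primary test. As written, a final p-value between 0.044 and about 0.048 counts as a failure, although the stated overall 0.05 would permit success. The Data Analysis Plan in Protocol section 10 also says that the primary outcome is tested at 5%. The general 0.05 rule in SAP 3.1.2 yields to specific sections, but that leaves 0.044 in force. A threshold chosen after a p-value had fallen in that gap would not be credible.

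**Working it through.** **Inputs.** Rates 60% and 35%, 2:1 allocation, 186 evaluable (62 + 124), 198 randomised (66 + 132), from SAP 2.6. Interim at information fraction 0.5, |Z| > 2.77 for efficacy and |Z| ≤ 0.44 for futility, from SAP 3.9. Levels 0.006 and 0.044, from SAP 3.7.1.

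**1. Reproduce the sample size.** For a single-look pooled test without continuity correction:

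- Mean rate = (0.60 + 2 × 0.35)/3 = 0.4333.
- SE under the null = √[0.4333 × 0.5667 × (1/62 + 1/124)] = 0.0771.
- SE under the alternative = √[0.24/62 + 0.2275/124] = 0.0755.
- Power at 0.05 = Φ[(0.25 − 1.960 × 0.0771)/0.0755] = Φ(1.31) = 90.5%.

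The minimum for 90% is 61 placebo patients (183 in total), so the stated 186 is reproduced within 3 patients. Attrition: 62/0.95 = 65.3, rounded up to 66, hence 198. The same formula at 0.044 (Z = 2.014) gives 89.5%.

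**2. Reproduce the boundaries.** A two-sided, two-look O'Brien-Fleming design with early rejection or acceptance (alpha 0.05, power 90%) gives interim bounds of 2.769 and 0.440, which are the plan's 2.77 and 0.44. Its final bound is about 1.958.

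**3. Overall alpha as written.** Under the null, the two Z statistics are bivariate normal with correlation √0.5. With final bound c and futility bound f (0 if ignored, 0.44 if obeyed):

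Overall alpha = P(|Z₁| > 2.77) + P(f < |Z₁| ≤ 2.77 and |Z₂| ≥ c).

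| Final bound c | Nominal p | Futility | Interim + final | Overall alpha |
|---|---|---|---|---|
| 2.014 | 0.044 | ignored | 0.0056 + 0.0407 | 0.0463 |
| 2.014 | 0.044 | obeyed | 0.0056 + 0.0388 | 0.0444 |
| 1.9795 | 0.0478 | ignored | 0.0056 + 0.0444 | 0.0500 |
| 1.9795 | 0.0478 | obeyed | 0.0056 + 0.0422 | 0.0478 |
| 1.9576 | 0.0503 | obeyed | 0.0056 + 0.0444 | 0.0500 |
| 1.9576 | 0.0503 | ignored | 0.0056 + 0.0468 | 0.0524 |

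In both rows that reach 0.0500, the final look spends 0.0444. That is where 0.044 belongs.

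**4. Power of the two-look rule at 60% against 35%.** Exact binomial enumeration with the pooled Z (equivalent to Pearson chi-square) and |Z| > 2.77 at the interim gives the figures below. Simulation of one million trials agrees to about 0.1 point.

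| Patients | Final rule | Futility obeyed | Futility ignored |
|---|---|---|---|
| 186 | 0.044 | 88.6% | 89.3% |
| 186 | matched bound | 90.1% (1.958) | 90.4% (1.98) |
| 198 | 0.044 | 90.6% | 91.6% |

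With the futility rule held constant, the loss from 0.044 at 186 is 90.1 − 88.6 = 1.5 points or 90.4 − 89.3 = 1.1 points. Normal approximations for 186 with 0.044 give 88.2% to 89.4% with futility obeyed and 89.2% to 90.4% with it ignored, depending on whether the drift uses the pooled or unpooled variance.

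**The case against.** **The pair may be alpha spent per look.** Rounded, 0.0056 and 0.0444 are exactly the plan's 0.006 and 0.044, and the final critical value may be in the boundary figure (Protocol Figure 1, SAP Appendix 5.7), which is not reproduced in the text available. The numerical match is right, and it explains where 0.044 came from. But SAP 3.7.1 names 0.044 as the level at which the final test is conducted, and an analyst following the text would use it as the cut-off. For the same reason, a reader should not infer that 0.044 contradicts the plotted boundary, since the text gives no final Z to compare.

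**Type I error is controlled.** This stands. A split that adds to 0.05 cannot exceed 0.05. A reader might infer an inflated false-positive rate, but the calculation shows the reverse.

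**The interim does not have two rules.** A reader might take |Z| > 2.77 and 0.006 as competing thresholds. Z = 2.77 is p = 0.0056, which is 0.006 to three decimals, and SAP 3.9 states the operative rule in Z.

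**The trial is not shown to be underpowered by this.** The primary analysis is intention-to-treat on all randomised patients. At 198 and the planned rates, power stays above 90% even with 0.044. If 5% drop out and count as failures while the rest follow the planned rates (an assumption), the rates become 0.05 + 0.95 × 0.60 = 62% and 0.05 + 0.95 × 0.35 = 38.25%, and power with 0.044 is about 87% to 88%. The matched bound recovers only about 1 point of that. The rest comes from counting dropouts as failures.

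**Conclusion.** The point holds as a conservative mismatch in a stated decision threshold. Used as a final p-value cut-off after |Z| > 2.77 at half information, 0.044 gives an overall two-sided alpha of about 0.046 (futility ignored) or 0.044 (futility obeyed) where the plan says 0.05. The matching nominal level is about 0.048 if futility is not binding. The cost is about 1 to 1.5 points of power at 186 evaluable patients, and none that brings the planned 198 below 90% at the planned rates.

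This rests on equal information at the two looks and on the large-sample normal approximation. The chi-square test is discrete, so its exact size differs slightly. With both arms at 60% and futility ignored, the 2.77/1.98 rule has size 0.0516 at 186 and 0.0492 at 198. The matching bound also depends on whether futility is binding, which neither document states.

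The change should be made, because it fixes the pass/fail line of the primary test and needs only wording. It does not threaten the validity of a positive result.

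**What to change.** In SAP 3.7.1, SAP 3.9 and Protocol section 10:

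- Keep |Z| > 2.77 (p < 0.0056) as the single interim efficacy rule.
- State that the 0.44 futility rule is non-binding. This fits the current text, under which crossing it leads only to a recommendation.
- Replace 0.044 with the matching final rule, |Z| > 1.98 (nominal p < 0.0478). If 0.006 and 0.044 are kept, label them as alpha spent at each look.
- Do not use |Z| > 1.958 unless futility is declared binding. If a futility crossing were overridden, that bound would give an overall alpha of 0.0524.
- Align the 5% statement in the protocol's Data Analysis Plan with the final rule.
- Restate power for the two-look design. With 2.77 and 1.98 it is about 90.4% at 186 if futility is ignored and about 89.7% if futility stops are followed. At 198 and the planned rates it is about 91.9% and 90.9%.

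The cost is wording in two documents, with no extra patients. The change should be made before any unblinded look at the primary endpoint.
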